Official Title of the Study: The Use of Fluorescent Imaging for Intraoperative Cholangiogram

during Laparoscopic Cholecystectomy

Document Date: August 1, 2014

NCT Number: NCT01424215

NEAR INRFARED FLUORESCENT CHOLANGIOGRAPHY: A RANDOMIZED CONTROL TRIAL

[name] MD FACS, [name] MD, [name] DO

Maimonides Medical Center, Division of Minimally Invasive Surgery, Brooklyn NY

Abstract

BACKGROUND: Bile duct injury (BDI) is the most feared complication encountered during laparoscopic cholecystectomy. Intraoperative cholangiography (IOC) has been shown to decrease the incidence of BDI yet has failed to become routine in the US. Fluorescent cholangiography using near infrared (NIR) imaging provides similar anatomic detail to radiographic cholangiography without some of the drawbacks.

METHODS: 50 patients undergoing laparoscopic cholecystectomy were randomized. 25 acted as the control group while the other 25 received 1cc of indocyanine green (ICG) intravenously prior to the procedure. Operative time, time to identification of the major structures and the surgeon's assessment of visualization, safety, teaching value and resident autonomy were evaluated.

RESULTS: No difference in mean operative times was noted between the control and ICG groups (46.1 and 52.4 minutes respectively) but mean time to identification of the key anatomical structures (19.7 and 14.2 minutes respectively) was significantly reduced. NIRC did not significantly improve the safety of the procedure or the ability of the surgeon to identify important structures but did allow the surgeon to give trainees

greater operative autonomy. Operative management was altered based on pinpoint imaging (4%) in 2 cases. There were no complications or leaks in this series.

CONCLUSION: The results of this study are encouraging and indicate that although NIRC does not supplant the critical view of safety technique it speeds recognition of key structures. It may be especially helpful for surgeons early in the learning curve to help in identifying anatomy and preventing injury and in teaching centers.

Methods: 50 consecutive patients undergoing laparoscopic cholecystectomy were enrolled in this study. Patients were randomized to either the study or control group using a sealed envelope system.

Prospectively collected data included demographics, indications for surgery, operative time, adequacy of cholangiographic images and any change in operative plan based on the NIR images.

Student's t test was used to compare groups and a difference considered statistically significant when P < 0.05. This study was approved by the ethics review board of our institution and registered with clinicaltrials.gov (Identifier#NCT01424215).

Underweight, normal weight overweight, obesity and severe obesity were defined using WHO guidelines¹. Patients were considered to have acute cholecystitis based on imaging (ultrasound or CT scan indicated a thickened wall and or pericholcystic fluid), elevated WBC count, physical exam (murphy's sign) and intraoperative findings.

Cholangiographic imaging was considered successful only in one of two scenarios:

- a. the common hepatic duct (CHD) and common bile ducts (CBD)
- b. the cystic duct (CD) and CBD/CHD fluoresced and were readily distinguishable from the surrounding areolar tissue. Dissection continued until this result was achieved.

Fluorophore - Indocyanine Green (Akorn, Lake Forest, IL): Intravenous ICG binds to plasma proteins, is taken up almost exclusively by the liver and is rapidly excreted in the bile². When exposed to near infrared light ICG fluoresces at a peak

wavelength of approximately 830 nm and can be imaged using a NIR camera. 1-3ml (2.5-7.5mg reconstituted) of ICG was injected via a peripheral IV catheter concomitant with induction of anesthesia. ICG can be seen in bile within minutes following intravenous injection and will continue to be evident even after a prolonged period of time.

NIR Fluorescent imaging system - PinpointTM (Novadaq, Ontario, Canada):

The Pinpoint system consists of a specialized endoscopic camera and light source capable of acquiring both high definition (HD) white light images and NIRC images simultaneously. These images can be displayed separately or as a composite of the NIRC image superimposed on the visible light HD image. This mode is especially useful because it provides context for the ICG cholangiogram thus allowing the user to more readily interpret the data (Figure 1).

Figure 1. Combined mode NIRC view (Cystic artery = arrow, Cystic Duct = arrowhead)

Of the 50 patients undergoing laparoscopic cholecystectomy 25 were randomized to receive indocyanine green (ICG) and 25 were randomized to the control group.

A standardized technique was used in all cases³. In summary, a 4 trocar technique was used, which includes a 12mm trocar placed in the supraumbilical region, an 11mm trocar in the subxiphoid region and 2 lateral 5mm trocars (Kii, Applied Medical, Rancho Santa Margarita, CA) for retraction. The camera was placed at the 12mm site and dissection carried out using the subxiphoid trocar. The combined imaging mode —which displays a composite image made up of the HD white light image and the superimposed real-time NIRC — was used as the sole imaging system in all cases (Video 1).

Operative time was calculated based on time from incision to skin closure. Time to identification of the structures was calculated from procedure start time until either the CHD and CBD or the CD and CBD/CHD were identified by the attending surgeon.

Dissection in all cases was performed by a surgical resident, while retraction and direction was provided by the attending surgeon.

In all cases the critical view of safety (CVS) as described by Strasberg⁴ was obtained prior to clipping and dividing any structure. Using electrocautery the gall bladder was separated from the gall bladder fossa and removed through the umbilicus using a specimen retrieval bag (Inzii, Applied Medical). An absorbable stitch was placed to close the fascial defect at the umbilicus followed by skin closure.

At the completion of the cases, the operative surgeon was asked to assess visualization, safety, teaching value of the case and resident autonomy on a five-point Likert Scale (Figure 2).

Postoperative Assessment

Visualization of structures	
Structures were visualized after extensive dissection-	Structures were immediately visualized
133	5
Safety	
Structures were at risk during dissection	Structures were safe throughout the dissection
133	5
Resident autonomy	
Procedure was performed entirely by the attending	Resident performed entire procedure
2333	5
Teaching value	
Teaching goals were not accomplished	Teaching goals were accomplished
133	5

Figure 2. Subjective postoperative assessment

All patients were followed up at least twice postoperatively, at one week and one month post discharge.

cial disclosures related to this study.

¹ World Health Organization, Report of a WHO Consultation on Obesity. Obesity: preventing and managing the global epidemic, Geneva: World Health Organization, 2000.

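### Does the 4% rate of altered operative management use the wrong denominator?

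*Combined protocol and SAP*

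**What the plan says.** The result appears once, in the RESULTS part of the abstract: "Operative management was altered based on pinpoint imaging (4%) in 2 cases". The supplied text has no fuller results section, and no other place reports this item or defines a denominator for it.

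The related statements are these:

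- **Size and arms.** The METHODS part of the abstract says "50 patients undergoing laparoscopic cholecystectomy were randomized" and then "25 acted as the control group while the other 25 received 1cc of indocyanine green (ICG) intravenously prior to the procedure". The Methods repeat the same split: "Of the 50 patients undergoing laparoscopic cholecystectomy 25 were randomized to receive indocyanine green (ICG) and 25 were randomized to the control group".
- **The item collected.** The list of prospectively collected data in the Methods includes "any change in operative plan based on the NIR images".
- **The source of the signal.** The fluorophore paragraph names one dye: "When exposed to near infrared light ICG fluoresces at a peak" wavelength of about 830 nm.
- **The imaging system.** The paragraph on the Pinpoint system describes a camera and light source "capable of acquiring both high definition (HD) white light images and NIRC images simultaneously".
- **Who was imaged.** The description of operative technique says that the combined mode "was used as the sole imaging system in all cases".

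**The concern.** A percentage with no stated denominator, in a two-arm trial, needs checking. Here the check shows that the two cases were divided by all 50 patients, controls included. The item collected is a change prompted by the near infrared images, and only half the patients are described as receiving the dye that fluoresces. If controls had no fluorescent duct signal, they could hardly have had their operation changed by one. Counting them in the denominator would then dilute the rate.

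What would be at stake is the size of the one figure in the supplied text that shows how often the imaging changed what the surgeon did. A reader could carry 4% forward as the rate under ICG when the rate in the patients given ICG was 8%. The terms also differ: the Methods speak of near infrared images and the result speaks of the Pinpoint system, so one might ask whether they describe the same event.

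**Working it through.** **Inputs.** Events: x = 2, with a printed rate of 4% (abstract, RESULTS). Group sizes: 50 in total, 25 ICG and 25 control (abstract, METHODS; repeated in the Methods).

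**Step 1. Reproduce the printed figure.** The rate is x/n.

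- 2/50 = 0.040 = 4.0%, an exact match.
- 2/25 = 0.080 = 8.0%, no match.

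To see how firmly this fixes the denominator, ask which n make 2/n round to 4%. At n = 44, 200/44 = 4.55, which rounds to 5. At n = 45, 200/45 = 4.44, which rounds to 4. At n = 57, 200/57 = 3.51, which rounds to 4. At n = 58, 200/58 = 3.45, which rounds to 3. So n lies between 45 and 57, and 50 is the only group size in the document within that range. The denominator is not printed, but the abstract lets the reader recover it.

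**Step 2. The rate if both cases were ICG patients.** The exact (Clopper-Pearson) 95% limits are the 0.025 quantile of Beta(x, n − x + 1) and the 0.975 quantile of Beta(x + 1, n − x).

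| Denominator | Rate | Exact 95% CI |
|---|---|---|
| 50, all randomized | 2/50 = 4.0% | 0.5% to 13.7% |
| 25, ICG arm, if both cases are there | 2/25 = 8.0% | 1.0% to 26.0% |

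Each interval contains the other point estimate. With two events, either presentation tells the reader only that such changes were uncommon and their frequency poorly known.

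**Step 3. Is 50 a sensible denominator?** Set the passages side by side. The result is attributed to Pinpoint imaging. The operative technique section says that the combined Pinpoint display was the only imaging used, in every case. The same section speaks of all cases when it describes the standardized technique, dissection by a resident and the critical view of safety, and those statements read as covering the whole series. Read the same way, all 50 patients were operated on under Pinpoint, and 2/50 is the rate among patients so imaged. The next sentence of the abstract, on complications and leaks, also reports on the whole series.

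**Step 4. Are the two terms two different events?** The Pinpoint system is introduced under a heading that calls it the near infrared fluorescent imaging system. Taking the reported result to be the collected item is the natural reading. The system also shows white light, but nothing in the text suggests that either change was prompted by that view.

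**Step 5. Where is the figure used?** It is set beside the abstract's count, is not compared between arms, and is not mentioned in the abstract's CONCLUSION. The comparisons of operative time and of time to identification do not depend on it.

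**The case for a change.** The strongest reply is that printing the count does not let the reader work out the rate under ICG, because the arm is missing. That is true. From the text alone the ICG-arm rate could be 0/25 = 0%, 1/25 = 4.0% or 2/25 = 8.0%. A result credited to the imaging in a randomized comparison is best shown by arm, and the supplied text offers no fuller report to consult.

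What stands is modest. The arm of the two cases is not given, and n/N by arm would be more informative. The three splits are not equally credible, however. A change based on near infrared images in a patient without ICG would itself need explaining, so 2 of 25 is what a reader would expect, although the document does not say it. Nor can one say in which direction the 4% misleads. It understates the ICG-arm rate if both cases were there, equals it if there was one in each arm, and overstates it if both were controls. The text also does not say whether the changes were beneficial, so a higher rate is not plainly to the credit of the device.

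The reply therefore shows a missing detail. It does not show a wrong number or a wrong analysis.

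**Conclusion.** The concern does not call for a change. The 4% is arithmetically right as 2/50, its denominator can be recovered from the abstract, and the Methods supply a reason for using all 50 patients. The most the point could move is one descriptive percentage, from 4.0% to 8.0%, on two events, with intervals that overlap widely (0.5% to 13.7% and 1.0% to 26.0%). No test, between-arm comparison or stated conclusion would differ.

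The 8.0% rests on an assumption that the document does not state: that both cases received ICG. The reading of 50 as coherent rests on taking the statement about the sole imaging system to include the control arm. If that statement was meant only for ICG patients, 25 would be the more natural denominator, but the printed figure would still be a correct proportion of all randomized patients. Anyone writing a fuller report would give the arm and the n/N for these two cases as a matter of course, from data already collected. That is ordinary reporting detail, and the planned analysis gains nothing from being altered to demand it.

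### The two operative timings are compared only by an unadjusted t test after allocation with no described stratification, so with 25 per arm a chance imbalance in acute cases could move the differences by a minute or two, and precision is lost

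*Combined protocol and SAP*

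**What the plan says.** All of this is in the Methods of the combined protocol and SAP, apart from the reported means, which are in the Abstract.

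- **Entry:** "50 consecutive patients undergoing laparoscopic cholecystectomy were enrolled in this study". No inclusion or exclusion criteria appear in the available text.
- **Allocation:** "Patients were randomized to either the study or control group using a sealed envelope system"; "25 were randomized to receive indocyanine green (ICG) and 25 were randomized to the control group". No stratification factor, block size or method of generating the sequence is described.
- **Baseline data:** "Prospectively collected data included demographics, indications for surgery, operative time". Weight class has a definition ("Underweight, normal weight overweight, obesity and severe obesity were defined using WHO guidelines"). So does acute disease ("Patients were considered to have acute cholecystitis based on imaging"), with white cell count, physical examination and intraoperative findings as further elements.
- **Analysis:** "Student's t test was used to compare groups and a difference considered statistically significant when P < 0.05". No covariate, stratified analysis or comparison of the arms at baseline is described.
- **Reported means, control v ICG:** time to identification 19.7 v 14.2 minutes, called significantly reduced; operative time 46.1 v 52.4 minutes, described as no difference. No standard deviations are given.

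**The concern.** Both timings depend on how hard the dissection is, and inflammation and obesity plausibly lengthen both. The investigators evidently expected these features to vary, since they defined categories for them, but the stated analysis makes no use of them. With 25 patients per arm, unstratified allocation can leave the arms visibly different in the share of acute cases. The t test neither corrects for such a difference nor removes case-mix variation from its error term. At stake is how much of the 5.5-minute reduction in time to identification, the main positive finding, can be attributed to the imaging, and how precisely either timing difference is estimated. Without a baseline table by arm, a reader cannot tell whether an imbalance occurred.

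**Working it through.** The plan gives no power calculation, target difference or standard deviation (SD), so it offers no figure of its own to reproduce.

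**Inputs from the document:** 25 per arm; P < 0.05 (two-sided assumed, since sidedness is not stated); differences of 19.7 − 14.2 = 5.5 minutes and 52.4 − 46.1 = 6.3 minutes.

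**Assumptions, not in the document:** 20-50% of patients acute; acute disease adds D = 5-10 minutes; within-stratum SD s = 8 minutes, with 10 as a check.

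**1. What the reported significance implies.** With 48 degrees of freedom the critical t is 2.011. A 5.5-minute difference is significant only if SD ≤ 5.5 / (2.011 × √(2/25)) = 9.67 minutes. Any scenario for time to identification should respect this bound.

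**2. Chance of imbalance.** With K acute patients among 50 and a random split into 25 and 25, the number in one arm is hypergeometric. The chance of a gap of at least 20 percentage points is:

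| Acute patients | Either direction | Favouring ICG |
|---|---|---|
| 10 (20%) | 7.4% | 3.7% |
| 15 (30%) | 21.7% | 10.8% |
| 20 (40%) | 14.8% | 7.4% |
| 25 (50%) | 25.8% | 12.9% |

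The figures do not rise steadily because gaps come in steps of 2/25 = 8 points. With K even, 20 points cannot occur and the next attainable gap is 24.

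**3. Size of the shift.** Shift = gap × D: 0.20 × 5 = 1.0 minute and 0.20 × 10 = 2.0 minutes, which is 18% and 36% of 5.5.

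**4. Could imbalance create the whole 5.5 minutes?** At D = 10 the gap would have to be 5.5 / 10 = 55 points, with probability of about 0.0001 or less at every prevalence above. At D = 5 it would have to exceed 100 points, which is impossible. Even at D = 15 it would have to be 37 points, with probability below 1%.

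**5. Error rate.** In 20,000 simulated trials per setting (prevalence 30% and 50%, total SD 9.67), the t test's type I error over all randomisations was 4.8-5.1%. Among trials with a gap of at least 20 points it was about 6.3% at D = 5 and 10.7% at D = 10. The model adjusted for acute status gave 4.5-5.0% in the same trials.

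**6. Precision.** The share of variance due to acute status is p(1 − p)D² / [p(1 − p)D² + s²]. At p = 0.3:

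- D = 10, s = 8: 21 / (21 + 64) = 25%. Total SD is √85 = 9.2, within the bound in step 1.
- D = 5, s = 8: 5.25 / 69.25 = 8%.
- D = 5, s = 10: 5.25 / 105.25 = 5%. Total SD is √105.25 = 10.3, above the bound, so this serves only as a low-end check.
- D = 10, s = 10: total SD is √121 = 11.0, so t = 5.5 / (11.0 × 0.283) = 1.77 and P = 0.08. This conflicts with the reported significance and is set aside.

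In the simulations, adjustment raised power for 5.5 minutes from about 0.50 to 0.60-0.63 at D = 10, but only to 0.51-0.53 at D = 5.

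**The case against.** The strongest reply is that the patients were randomised, so an unadjusted t test is a valid and common choice in a 50-patient trial, and no imbalance has been shown. The first part stands: overall type I error is about 5%, and what remains is conditional error and lost precision. A reader might infer that the results are confounded by case mix. The document does not support that, because any imbalance here would be due to chance and none is documented.

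A reader might also infer that case mix explains both timing differences. It cannot. If acute disease lengthens both timings, an excess of acute controls would flatter ICG on identification but would also lengthen operative time in the control arm, and that time was shorter. An excess of acute ICG patients could contribute to the longer ICG operative time, but the benefit on identification would then be understated. The report also makes no positive claim on operative time.

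It is fair to add that the magnitudes rest on an assumed prevalence and effect, and that the gain is small if acute disease adds only 5 minutes. The spread of the population is likewise inferred from the category definitions and the absence of eligibility limits. No counts are given, and the document never describes its patients as elective. Part of the text is cut off, so the statement is only that no stratification or adjustment is described in what is available.

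**Conclusion.** The concern holds as a matter of precision and conditional error, not of bias. If 20-50% of patients were acute, an imbalance of 20 points or more has a probability of about 7-26%, roughly half of it in ICG's favour. If acute disease adds 5-10 minutes, such an imbalance moves the difference by 1-2 minutes. That is a material part of 5.5 minutes but very unlikely to be all of it. The variance recoverable by adjustment is about 25% at best in the scenarios consistent with the reported significance, and 5-8% if the effect of acute disease is weak. Which case applies cannot be settled without acute status by arm and the standard deviations. The data needed are largely recorded already, so the analysis is worth doing, although its absence does not invalidate the trial.

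**What to change.** 1. Tabulate acute status and BMI (or WHO weight class) by arm.
2. Report beside the t test a linear model for time to identification, and another for operative time, with arm, acute status and BMI (or weight class). Give adjusted differences with 95% confidence intervals. Label both models post hoc: the results are already known, so they should not replace the stated test.
3. Define acute status for this purpose from imaging, white cell count and physical examination only. The documented definition also draws on intraoperative findings, which arise after randomisation and should not enter a baseline covariate.
4. For any further enrolment, use blocked sealed envelopes stratified by preoperative acute status and keep that factor in the model. Separate envelope sets without blocking would not secure balance within strata.

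The cost is two degrees of freedom out of 50 patients (more if weight class is entered as categories), some recoding of acute status from the records, and the possibility that the adjusted difference is less favourable than the raw one.

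### Imaging adequacy has no failure branch: if the stated rule is followed, every ICG case is recorded as a success, so the outcome cannot show how well ICG images the ducts

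*Combined protocol and SAP*

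**What the plan says.** **Imaging adequacy.** The Methods paragraph on prospectively collected data includes "adequacy of cholangiographic images and any change in operative plan" based on the NIR images. The later Methods paragraph on successful imaging accepts two scenarios: (a) common hepatic duct and common bile duct, or (b) cystic duct with common bile or hepatic duct. The structures must fluoresce and stand out from the surrounding tissue. That paragraph ends: "Dissection continued until this result was achieved". No fixed assessment point, time limit or failure category is given.

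Only one arm can fluoresce. The abstract's METHODS say that "25 acted as the control group while the other 25 received 1cc of indocyanine green (ICG) intravenously prior to the procedure".

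**Autonomy.** The abstract's RESULTS say that NIRC "did allow the surgeon to give trainees" greater autonomy. The only source described for this is the end-of-case form, on which "the operative surgeon was asked to assess visualization, safety, teaching value of the case and resident autonomy on a five-point Likert Scale". The caption of Figure 2 calls the form subjective. The composite display with the NIR overlay "was used as the sole imaging system in all cases". Allocation was by sealed envelope; no masking and no independent rater are described.

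**Results that bear on both.** Time to identification ran "until either the CHD and CBD or the CD and CBD/CHD were identified by the attending surgeon". The abstract also reports that "NIRC did not significantly improve the safety of the procedure or the ability of the surgeon to identify important structures".

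**The concern.** An outcome that measures how well an imaging method works must be able to fail. Here the work that precedes the assessment goes on until the assessment is positive. The recorded result then shows that dissection was carried far enough, not that ICG displayed the ducts well. In a trial of an imaging method, a reader given an adequacy rate would naturally take it as imaging performance.

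The autonomy sentence matters for a different reason. It is one of two positive comparative results in the abstract; the other is time to identification, 19.7 minutes in controls and 14.2 with ICG. It is worded as something the imaging did, while what was collected is a rating by a surgeon who directed the case and could see the overlay.

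**Working it through.** **Step 1: can the adequacy outcome fail?** Set the three statements side by side.

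- Adequacy is a collected item (Methods, data collected).
- Adequate means that (a) or (b) fluoresces and is distinguishable (Methods, definition of success).
- Dissection goes on until that holds (same paragraph).

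The third statement makes the second true at the end of every case that follows the rule. A failure could be recorded only if the rule was not followed, for example if dissection ended before fluorescence was adequate. The plan does not say how such a case is counted.

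**Step 2: to whom does it apply?** The criterion needs fluorescence and controls received no ICG, so it applies to the 25 ICG cases only. The recorded rate under the rule is 25/25 = 100%.

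**Step 3: how much information is lost?** The documents give no first-view counts, so the counts below are assumptions covering a wide range. The intervals are exact (Clopper-Pearson) 95% intervals for x of n = 25. The lower limit is the 0.025 quantile of Beta(x, n − x + 1) and the upper limit is the 0.975 quantile of Beta(x + 1, n − x). For x = 25 the lower limit is 0.025^(1/25) = 0.863 and the upper limit is 1.

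| Criterion met at first view (assumed) | Proportion | Exact 95% CI | Recorded under the rule |
|---|---|---|---|
| 5/25 | 20% | 7% to 41% | 25/25, 86% to 100% |
| 10/25 | 40% | 21% to 61% | 25/25, 86% to 100% |
| 15/25 | 60% | 39% to 79% | 25/25, 86% to 100% |
| 20/25 | 80% | 59% to 93% | 25/25, 86% to 100% |

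Four very different imaging performances give the same record, and its interval excludes all four first-view proportions. The conclusion comes from step 1 and does not depend on the assumed counts.

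**Step 4: do other outcomes fill the gap?** Time to identification uses the same duct combinations, but it ends when the attending identifies them, and fluorescence is not required. The Visualization item in Figure 2 grades how much dissection was needed before structures were seen. Both carry some information on early visibility. Neither records whether (a) or (b) fluoresced at a fixed point.

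**Step 5: does the rule damage time to identification?** No. That outcome is defined separately, applies to both arms and can vary from case to case.

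**Step 6: the autonomy sentence.** The chain is one item of four, one rating per case, given by the operative surgeon after the case, on a form labelled subjective, with the overlay on display throughout. Presence or absence of fluorescence would ordinarily reveal the arm. This establishes that the rating was open to influence from knowledge of allocation. Nothing in the documents shows a shift or its direction. No autonomy scores or standard deviations are given, so no size can be calculated for this trial.

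**The case against.** **On adequacy.** Adequacy is not among the outcomes that the abstract says were evaluated, no adequacy rate is given, and no conclusion rests on it. The trial is reported as complete, so a first-view record cannot now be created for cases that lack one. The definition says imaging counts as successful only in the two scenarios, which suggests that failure was contemplated. Every case also had to reach the critical view of safety, so dissection had another end point. The choice of first view is a judgement, and it asks a narrower question than a criterion that allows dissection.

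Much of this stands. It limits the consequence but does not remove the defect: adequacy is still a named outcome, and the text still gives it no way to fail. A reader might infer that the trial reported an empty 100% success rate, or that the shorter time to identification is a product of the rule. The documents support neither. No rate is reported in the available text, and the time outcome is defined independently of fluorescence.

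**On autonomy.** Allocation was randomised, which supports comparing the ratings. Seeing the overlay is the intervention, so the surgeon could hardly be masked. The anchors of the item refer to who performed the procedure, which is partly observable. The same abstract reports no significant improvement in safety or in the surgeon's ability to identify structures, which weighs against general inflation of ratings. It does not exclude a shift confined to autonomy, and the abstract does not say whether the identification result comes from the Visualization item.

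A reader might infer that the autonomy result is biased or false. The documents do not show that. One can assume a rating shift of 0.1 to 0.5 points and a standard deviation of 0.5 to 1.0, and calculate how often a t test with 25 per arm gives P < 0.05 with no true effect. The answer runs from about 6% to 93%. Every input is assumed, so the range is no evidence about this trial.

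**Conclusion.** The adequacy point holds, on the condition that the stated rule was followed. Any adequacy rate would then be 100% by construction and would say nothing about how well ICG images the ducts. It restricts what this outcome can show; it does not overturn a reported result and does not touch the time-to-identification comparison. Only the abstract and Methods are available, so whether failures of imaging were reported elsewhere cannot be determined.

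The autonomy point is secondary and concerns wording. The randomised comparison of ratings can be reported as such. The causal phrasing goes further than a single subjective item with no masking described will bear. Time to identification shares part of this limitation, because an attending surgeon who could see the overlay called it.

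**What to change.** **Adequacy.**

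- In each ICG case, record yes or no: does (a) or (b) fluoresce at one fixed point, the first view before dissection?
- Count non-success at that point as a failure out of all 25 ICG cases.
- Report separately any case that never meets the criterion.
- Where the first view was not recorded, present no adequacy rate.

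How dissection is done does not change. The cost is one extra record per ICG case and a possibly lower success rate. For completed cases without the record, the outcome has to be left unreported.

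**Autonomy.** Replace the causal sentence in the abstract with: *the operating surgeon, with no masking to allocation described, rated resident autonomy higher in the ICG group.* Add one sentence stating that time to identification was also called by an attending surgeon who could see the overlay, and that neither safety nor the surgeon's ability to identify structures was significantly improved. Keep to *not significantly improved*; the abstract does not say that these did not differ. The cost is a weaker result sentence and a limitation that also qualifies the time result.
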